5.3.4 Guidelines for Safety Monitoring

[figure not shown]
Monitoring of a key safety endpoint will be conducted monthly, and if rates significantly exceed pre-set thresholds, the NHLBI will be notified in order that the DSMB can be advised. Policies and composition of the DSMB are described in the BMT CTN's Manual of Procedures. The stopping guideline serves as a trigger for consultation with the DSMB for additional review.

Safety monitoring will be based on Day 56 NRM. The proportion of NRM based on historical controls is estimated to be 20% versus an alternative hypothesis of 40%. This outcome will be monitored up to 56 days post-randomization, separately in each treatment arm, using a truncated Sequential Probability Ratio Test (SPRT) for binary data resulting in decision boundaries with a common slope of 0.293 and an upper intercept of 2.679 with nominal type I and type II error rates of, 0.065 and 0.10, respectively.

This sequential testing procedure conserves type I error at 5% across all the monthly examinations. The SPRT can be represented graphically. At each monthly examination, the number of evaluable patients is plotted against the cumulative sum of the endpoint of interest. The continuation region of the SPRT is defined by two parallel lines. Only the upper boundary will be used for monitoring to protect against excessive Day 56 NRM. If the cumulative sum of the endpoint falls above the upper boundary, the SPRT rejects the null hypothesis, and concludes that there are more events than predicted by the observed number of patients evaluable. Otherwise, the SPRT continues until enrollment reaches the target sample size of 68 patients per arm. Table 5-4 and Figure 5-2 gives the rejection boundaries for the number of events for Day 56 NRM corresponding to the number of evaluable patients. As an example, if there are 15 evaluable patients with the number of Day 56 NRM being 8 or more, then this would trigger a review by the DSMB. Note that, at least four events must be observed to trigger review.

Table 5-4 Sequential Monitoring Plan for 68 Subjects per Arm ($\alpha = 0.065$, $\beta = 0.10$, $p_0 \leq 0.20$, $p_1 \geq 0.40$)

Number of Evaluable Patients	Rejection Boundary for the Null for the No. of Day 56 NRM	Number of Evaluable Patients	Rejection Boundary for the Null for the No. of Day 56 NRM	Number of Evaluable Patients	Rejection Boundary for the Null for the No. of Day 56 NRM
1-3		22-24	10	46-48	17
4	4	25-27	11	49-52	18
5-7	5	29-31	12	53-55	19
8-11	6	32-35	13	56-59	20
12-14	7	36-38	14	60-62	21
15-18	8	39-42	15	63-65	22
19-21	9	43-45	16	66-68	23

Figure 5-2 Acceptance and Rejection Boundaries for Safety Monitoring

The actual operating characteristics of the SPRT, shown in Table 5-5, were determined in a simulation study that assumed a uniform accrual of 68 patients to each arm over a 36-month accrual period.

Table 5-5 Operating Characteristics of the Sequential Probability Ratio Test for Day 56 NRM with 100,000 Simulation Replicates

True Day 56 NRM Rate	20%	25%	30%	35%	40%
Probability Reject Null	0.051	0.200	0.481	0.768	0.935
Mean No. of Day 56 NRMs	13.1	15.0	14.9	12.9	10.5
Mean No. of Patients Enrolled	66	60	50	37	26
Mean No. of Months	36	33	27	20	15

For example, the testing procedure rejects the null hypothesis in favor of the alternative 5.1% of the time when the true Day 56 rate is 20% and 93.5% of the time when the rate is 40%. When the true Day 56 NRM rate is 40%, a review will be triggered when 10.5 events have been observed in 26 patients over a 15-month period.

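### Protocol Table 5-4 omits the Day 56 NRM review boundary at 28 evaluable patients; the protocol's own SPRT line gives 11 events

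*Protocol*

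**What the plan says.** Protocol 5.3.4 (Guidelines for Safety Monitoring) sets a null Day 56 NRM rate of 20% against an alternative of 40%, with "nominal type I and type II error rates of, 0.065 and 0.10, respectively". This gives "decision boundaries with a common slope of 0.293 and an upper intercept of 2.679". Each arm is monitored separately. "At each monthly examination, the number of evaluable patients is plotted against the cumulative sum of the endpoint of interest", and only the upper line is used. Without a crossing, "the SPRT continues until enrollment reaches the target sample size of 68 patients per arm".

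The text then says that Table 5-4, together with Figure 5-2, "gives the rejection boundaries for the number of events for Day 56 NRM corresponding to the number of evaluable patients". Its worked example fixes the convention: with 15 evaluable patients, 8 or more events lead to DSMB review. It also notes that fewer than four events can never trigger a review, which accounts for the blank entry at 1-3 patients.

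The middle column of Table 5-4 reads 22-24: 10, 25-27: 11, 29-31: 12, 32-35: 13. The count 28 appears in no row.

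SAP 7.8.2 (Statistical Monitoring Rules) refers to Protocol 5.3.4 for the scheme and gives no boundary table of its own.

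**The concern.** The check is monthly, so the number of evaluable patients at a check can be any value up to 68, including 28. The table is the form in which most users will apply the rule, because it converts the line into whole events. At 28 it gives them nothing: they can carry 11 forward, take 12 from the next row, or conclude that no threshold applies. Only the first agrees with the line.

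The case at stake is an arm with exactly 11 non-relapse deaths among 28 evaluable patients that had not crossed earlier. The line calls for DSMB review. A user who took 12, or no threshold, would wait for a later check, by which time the boundary is at least 12.

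**Working it through.** **Inputs** (Protocol 5.3.4): p0 = 0.20, p1 = 0.40, α = 0.065, β = 0.10, at most 68 patients per arm.

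**Step 1. Reproduce the stated line.**

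- D = ln[p1(1−p0) / (p0(1−p1))] = ln(0.32/0.12) = 0.9808
- Slope = ln[(1−p0)/(1−p1)] / D = ln(0.8/0.6) / 0.9808 = 0.2877/0.9808 = 0.2933
- Upper intercept = ln[(1−β)/α] / D = ln(0.9/0.065) / 0.9808 = 2.6280/0.9808 = 2.679

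Both agree with the protocol's "common slope of 0.293 and an upper intercept of 2.679".

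**Step 2. Confirm the convention.** The boundary is the smallest whole number above the line. At 15 patients the line is 2.679 + 0.293 × 15 = 7.07, so the boundary is 8, as in the worked example.

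**Step 3. Apply it around the gap.**

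| Evaluable patients | Line, stated constants | Line, unrounded constants | Boundary | Table 5-4 |
|---|---|---|---|---|
| 27 | 10.590 | 10.599 | 11 | 11 |
| 28 | 10.883 | 10.892 | 11 | no entry |
| 29 | 11.176 | 11.185 | 12 | 12 |

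Rounding of the constants does not affect the answer at 28, and the next row is right to start at 29.

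**Step 4. Check the rest of the table.** There are 65 counts from 4 to 68. The table lists 64, and every one agrees with the line under either set of constants. At 1 to 3 patients the line lies between 2.97 and 3.56, so no crossing is possible for 2 or 3 patients (4 events needed) or for 1 patient (3 needed). That blank is correct.

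**Step 5. Size of the effect.** The probability of crossing was computed by exact recursion to 68 patients, with a check after every patient, first with 11 at 28 and then with no check at 28. Using 12 at 28 gives the same result as no check: an arm with 12 events at 28 had at least 11 at 27 and had already crossed.

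| True Day 56 NRM | Table 5-5 | 11 at 28 | 28 skipped | Loss (points) |
|---|---|---|---|---|
| 20% | 0.051 | 0.0511 | 0.0504 | 0.07 |
| 25% | 0.200 | 0.1992 | 0.1975 | 0.16 |
| 30% | 0.481 | 0.4802 | 0.4784 | 0.18 |
| 35% | 0.768 | 0.7700 | 0.7690 | 0.10 |
| 40% | 0.935 | 0.9358 | 0.9354 | 0.03 |

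The column with 11 at 28 reproduces the protocol's simulated Table 5-5 to within 0.2 points. The two columns are too close for Table 5-5 to prove which was used, but it is consistent with 11.

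**Step 6. Monthly checks.** As an illustration, assume even accrual of 68 patients over 36 months, with one check per month and the evaluable count rounded down. Month 15 gives 68 × 15/36 = 28.3, so a check falls on 28. Skipping it lowers the crossing probability by 0.13, 0.31, 0.35, 0.21 and 0.07 points at true rates of 20, 25, 30, 35 and 40%. On this schedule the boundary is crossed for the first time at 28 in 0.4% of arms at a true rate of 20% and 6.4% at 40%. At 40%, then, nearly all of the arms whose crossing at 28 is skipped still cross later (6.4% against a loss of 0.07 points).

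**The case against.** The strongest reply is that nothing is missing from the rule. Section 5.3.4 gives the slope, the intercept and the instruction to reject above the upper line, and it describes the monthly check as a plot. With these, 28 patients and 11 events is a crossing, since 11 exceeds 10.88. Figure 5-2 is also cited for the boundaries; it is not reproduced in the text available here, but a plotted straight line would have no gap. A crossing leads to consultation with the DSMB and does not close enrollment, and the DSMB sees other safety data at each meeting. All of this stands, and it limits the point to the table.

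Three stronger readings are tempting, and the documents do not support them.

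- A reader might infer that the protocol literally provides no trigger at 28, by analogy with the blank at 1-3. But that row is printed with a blank boundary and explained in the text, whereas 28 is simply absent, and the stated line does give a trigger there.
- A reader might infer that the SAP adopts the faulty table. SAP 7.8.2 cites the whole of Protocol 5.3.4, which includes the line, and does not name Table 5-4.
- A reader might measure the effect by how often a check lands on 28, which is roughly half of arms at 68/36 = 1.9 patients per month. That is the frequency of the look. The omission matters only if that look also finds exactly 11 events with no earlier crossing, and the user does not consult the line.

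Could the gap come from the conversion of the PDF? The neighboring columns run on without loss across the same rows (4 to 5-7, and 49-52 to 53-55), so a dropped row is not the explanation. A single misread digit cannot be excluded from the text alone; a look at the printed table settles it.

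**Conclusion.** The point holds as a correction to the table. Table 5-4 lacks an entry for 28 evaluable patients, the protocol's own line puts the boundary there at 11, and no other table in either document supplies it. The pattern, with 64 of 65 counts correct, suggests a range typed as 25-27 in place of 25-28, not a miscalculation. It does not amount to a gap in the stopping guideline itself.

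The loss in the probability of triggering review is at most about 0.2 percentage points with a check after every patient, and at most about 0.35 points on the illustrative monthly schedule. The second figure assumes even accrual and a check that falls on 28; a schedule that misses 28 is unaffected. The practical consequence is a possible delay in consulting the DSMB in an arm with excess mortality. That is minor, but worth removing from a safety table.

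**What to change.** In Table 5-4, change the row 25-27: 11 to 25-28: 11. Confirm that the program that runs the monthly check uses 11 at 28 evaluable patients, and that it was not built by reading in the printed table. The cost is one table cell and one check of code. The slope, intercept, error rates and the other rows stay as they are, and Table 5-5 need not be simulated again.

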5.3.5 Safety Analysis

The reporting of serious adverse events is described in detail in Section 4.4.4.2. All reported serious adverse events potentially associated with study drug will be carefully examined with respect to the severity and relationship to study drug. The type and severity of adverse events will be described.

5.4 Demographic and Baseline Characteristics

Demographics and baseline characteristics will be summarized for all patients. Characteristics to be examined are: age, gender, race/ethnicity, performance status, primary disease, time from steroid initiation to randomization, acute GVHD grade at enrollment, MN classification, graft

source, GVHD prophylaxis, conditioning regimen, time from disease diagnosis to transplant, time from GVHD onset to randomization.

5.5 Analysis Populations

5.5.1 Primary Analysis Population

The intention-to-treat population will serve as the population for the primary analysis. All randomized subjects will be included in this population. Subjects will be included in the treatment group to which they are randomized. Intention-to-treat population consists of all randomized subjects whether or not treatment was administered. Any subject who receives a treatment randomization assignment will be considered to have been randomized. Analyses for the primary and secondary endpoints will use the primary analysis population.

5.5.2 Safety Analysis Populations

The safety analysis population in this study will comprise of all patients “as treated” in the study. This population will be used for the analysis of safety data. The “as treated” population consists of all randomized subjects who received at least one dose of study treatment. Subjects will be included in the treatment group corresponding to the study treatment they received for the analysis of safety data using the “as treated” population. For most subjects this will be the treatment group to which they are randomized. Subjects who take incorrect study treatment for the entire treatment period will be included in the treatment group corresponding to the study treatment received. Any subject who receives the incorrect study medication for one cycle but receives the correct treatment for all other cycles will be analyzed according to the correct treatment group and a narrative will be provided for any events that occur during the cycle for which the subject is incorrectly dosed.

5.5.3 General Analysis Guidelines

Primary analyses for the primary, secondary, and exploratory endpoints will use the primary analysis population except when otherwise specified. Analyses of each endpoint in each population will follow the analysis plans as described below in Sections 5.6, 5.7, and 5.8. We expect minimal missing data (< 5%) for the primary endpoint and secondary endpoints based on the past experience with a large phase III aGVHD treatment trial (BMT CTN protocol #0802. All secondary and exploratory analyses will use a two-sided significance level of 5%.

5.6 Analysis of Primary Endpoint

The response rate (CR/PR) at Day 28, compared to maximum GVHD organ staging within 72 hours prior to enrollment, is expected to be different by centers and GVHD risk (Group A vs Group B; see Section 2.4.1, #3). Therefore, we will fit a generalized linear mixed model with the response rate (CR/PR) at Day 28 as the outcome, treatment group as the main effect, and adjusted for GVHD risk fixed effect and center-specific random effects. A one-sided significance level of 2.5% will be used. The response rate (CR/PR) at Day 28 will be estimated using frequencies in each group along with corresponding 95% confidence intervals.

We plan on conducting two sensitivity analyses to assess the robustness of our findings. First, using the above generalized linear mixed model we will adjust for GVHD risk, age (adolescent vs adults) and disease (malignant vs non-malignant) all as main effects, in addition to

center specific random effects. The second analysis will include all the covariates from the first analysis in addition to the Mount Sinai Acute GVHD International Consortium (MAGIC) biomarker score. These two models will be compared to the primary analysis model in order to assess the impact on the main effect estimate.

5.7 Analysis of Secondary Endpoints

5.7.1 Duration of Response

Duration of response will be evaluated at 6- and 12-months post-randomization in the cohort of patients who achieve a Day 28 response. There will be a primary and secondary analyses of DOR. In the primary analysis, DOR is defined as the time from Day 28 response to progression, new salvage therapy for acute GVHD, death from any cause, or re-escalation of steroids to ≥ 2.5 mg/kg prednisone or equivalent. Patients without any of these events will censored at last follow up. For the secondary analysis, DOR will be defined as time from Day 28 response to death from any cause or new salvage therapy. Otherwise, patients are censored. For each definition, the probabilities of DOR will be estimated using the Kaplan-Meier method and compared between treatment arms using the log-rank test.

5.7.2 Non-relapse Mortality

Non-relapse mortality at 6 months and 12 months post-randomization will be estimated using the cumulative incidence function, treating relapse as a competing risk. The cumulative incidence curves for non-relapse mortality will be compared between the treatment groups using Gray's test. A Cox proportional hazards regression model with mixed effects will be used to compare the cause specific hazards of NRM between treatment groups adjusting for GVHD risk with center-specific log-normal frailties.

5.7.3 Overall Survival and Progression-Free Survival

Progression-free survival (PFS) at 6- and 12-months post-randomization will be estimated using the Kaplan-Meier method, treating death or relapse of malignancy as events in patients with malignancies. Overall Survival (OS) at 6 and 12 months will also be estimated using the Kaplan-Meier method. These endpoints will be compared between the treatment groups using the log-rank test. A Cox proportional hazards regression model with mixed effects will be used to compare PFS and OS between treatment groups adjusting for GVHD risk with center-specific log-normal frailties.

5.7.4 GVHD-Free Survival

The proportion of patients surviving at Day 56 after randomization without acute or chronic GVHD and without other systemic agents (or escalation of steroids to ≥ 2.5 mg/kg/day of prednisone [or methylprednisolone equivalent of 2 mg/kg/day]) added for treatment of GVHD will be evaluated. Provided there is no censoring prior to 56 days, this endpoint we will be computed as a binary outcome and summarized using frequencies/proportions. GVHD-Free survival will be compared by treatment adjusting for GVHD risk and center-specific random effects using a generalized linear mixed model. Additionally, treatment groups will be compared using difference in proportions, relative risk and an odds ratio estimate along with corresponding

confidence intervals. Censoring before 56 days is highly unlikely; and should this occur we anticipate this will be minimal.

5.7.5 Proportion of Response

The proportions of patients with Complete Response (CR), Partial Response (PR) (including subset with “Very Good Partial Response” [VGPR]), and Treatment Failure (TF) at Days 7, 14, 21, 28, 56 and 86 post-randomization will be described and compared between the treatment groups using the chi-square test or Fisher’s exact test as appropriate.

5.7.6 Proportion of Response (Next-Line Therapy)

The proportions of patients with CR, PR (including subset with VGPR), and treatment failure (TF) at Days 7, 14, 21, 28, 56, and 86 post-randomization who receive ruxolitinib or other next-line therapies approved by the protocol Chairs as next-line therapy and remain on AAT/PTM will be described and compared between the treatment groups, to evaluate any differences in safety and efficacy, using the chi-square test or Fisher’s exact test as appropriate. The proportion of AE/SAE will be described in these patient populations.

5.7.7 Systemic Infections

Frequencies of grade 2 or 3 infections occurring from randomization until 30 days after last study drug or placebo treatment will be tabulated by site of disease, date of onset, and severity. The time to first serious (grade 2 or 3) infection will be described using the cumulative incidence function and compared between treatment groups using Gray’s test, with death treated as a competing risk.

5.7.8 Adverse Events

Frequencies of grade 3-5 adverse events (per CTCAE Version 5.0) that occur from randomization through 30 days after completing study drug or placebo treatment will be tabulated using the Safety Population. The proportion of patients experiencing grade 3-5 adverse events will be compared between the treatment groups using an odds ratio estimate with confidence interval.

5.7.9 Chronic GVHD

The incidence of chronic GVHD will be computed at 6- and 12-months post- randomization using the cumulative incidence method, treating death prior to chronic GVHD as a competing risk. Diagnosis of chronic GVHD of any severity (mild, moderate, or severe) per NIH Consensus Criteria (see APPENDIX C) is considered an event for this endpoint. Cumulative incidence will be compared between treatment groups using Gray’s test. Cause specific hazard for chronic GVHD will be compared by treatment adjusting for GVHD risk and center-specific random effects using a generalized linear mixed model.

5.7.10 Disease Relapse

Disease relapse will be summarized at 6- and 12-months post-randomization using the cumulative incidence function with death as a competing risk. Cumulative incidence will be compared between treatment groups using Gray’s test. Cause specific hazards for disease relapse will be compared by treatment adjusting for GVHD risk and center-specific random effects using a Cox proportional hazards model with center specific log-normal random effects.

5.8 Analysis of Exploratory Endpoints

5.8.1 AAT Levels

The pharmacokinetics parameters maximum (C_{max}) and trough (C_{trough}) serum antigen concentration of AAT will be measured and summarized using descriptive statistics at Days 0, 8, 16, 24, 28 and 56 post-treatment initiation.

5.8.2 Stool AAT, Microbiome and Metabolome

Stool concentrations of AAT will be measured and summarized using descriptive statistics at baseline and Days 8 and 28 post-treatment initiation.

5.8.3 Immune Subsets

The changes in peripheral blood ratios of T regulatory to T effector (Treg/Teff) cells, Natural Killer (NK) cells and other cellular immune subsets from baseline to Days 16, 28, and 56 post-treatment initiation will be summarized using descriptive statistics at each time point and compared between treatment groups using Mann-Whitney nonparametric tests. Select immune subsets may also be analyzed using a linear mixed model adjusting for baseline value, time and treatment, as well as a treatment by time interaction term.

5.8.4 Inflammatory Cytokines and GVHD Biomarkers

Serum levels of inflammatory cytokines (e.g., IL-1 β , IL-6, IL-10, TNF α), damage associated molecular patterns (e.g., heparan sulfate) and select GVHD biomarkers (eg, ST2, REG3 α) at baseline and at Days 8, 28, and 56 post-treatment initiation will be summarized using descriptive statistics at each time point and compared between treatment groups using Mann-Whitney nonparametric tests. Select measurements may also be analyzed using a linear mixed model adjusting for baseline value, time, and treatment, as well as a treatment by time interaction term.

5.8.5 Overall and Organ-Specific Response Rates by Refined Minnesota Risk and Biomarker-Based Risk Classifications

The proportions of patients with an overall response (complete or partial) and response rate of each GVHD target organ at Day 28 post-randomization will be described by Refined Minnesota risk category (A vs B; see Section 2.4.1, #3) and by Ann Arbor biomarker risk score (1, 2, or 3) using sample proportions and confidence intervals and compared on each factor using the chi-square test or Fisher's exact test as appropriate.

5.8.6 Systemic Corticosteroid Dose

The systemic corticosteroid-dose (measured as prednisone-equivalent) will be summarized at baseline and at Days 7, 14, 21, 28, 56, 86, 6 months and 12 months post-randomization using descriptive statistics at each time point and compared between treatment groups using Mann-Whitney nonparametric tests.

